3.0.3 INCLUSION/EXCLUSION CRITERIA

Study Population Being Recruited	Inclusion Criteria:	Exclusion Criteria:
Youth involved in juvenile	Involved in juvenile drug court	Diagnosed with intellectual disability
drug court	Ages 13-17 years old at enrollment	or autism spectrum disorder.
	Teen willing to participate	
	At least one caregiver willing to	
	participate in treatment	
	Live in San Antonio	

Version: 2017 09 06 Page 10 of 45

	Fluent in English or Spanish	
Caregivers of youth involved in juvenile drug court	Caregivers of youth involved in juvenile drug court Caregiver willing to participate Lives in San Antonio Fluent in English or Spanish	Diagnosed with intellectual disability or autism spectrum disorder
Counselors providing substance abuse treatment services to youth involved in juvenile drug court	Counselor providing substance abuse treatment to an adolescent involved in drug court	N/A
juvenile drug court personnel	Juvenile drug court supervisors and probation officers working in Bexar County Juvenile Drug Court	N/A

3.0.4 RANDOMIZATION PROCESS

Caregivers and youth willing to participate will be consented and either complete study entry assessments and randomization or will be consented and then scheduled for an appointment for completion of study entry assessments and randomization at a more convenient time. Caregivers and youth will be randomized to either the caregiver contingency management or treatment as usual group. The proposed urn randomization procedure is a randomization method that aims to achieve balance across groups on factors that, if unaddressed, could bias estimates of the intervention effect. There is an exception to the randomization procedure. Some families will be placed into the caregiver contingency management group for the purpose of training therapists prior to receiving randomized participants.

4.0 RESEARCH DESIGN & METHODS Design Overview:

A well-specified intervention, Contingency Management, will be adapted to reinforce caregiver participation in drug court (CCM). We propose a randomized clinical trial examining the utility of caregiver contingency management to increase caregiver engagement in juvenile drug court and adolescent drug treatment activities. The proposed study follows a 2 (treatment type: Drug Court plus treatment as usual (TAU); Drug Court and TAU plus Caregiver CM [CCM] x 10 (time: pretreatment [T0], 1-month [T1], 2-month [T2], 3-months [T3], 4-month [T4], 5-month [T5], 6-months [T6], 9-months [T7], 12-months [T8], and 18-months [T9-six months post-juvenile drug court involvement]) factorial design, with random assignment of 180 caregivers/youths to one of the two treatment conditions. Repeated measures of caregiver and youth functioning will be collected at pre-treatment (T0), and each of the post-randomization time points (T1 – T9). We choose a randomized trial because this is the most valid way to test the efficacy of our proposed intervention. We choose the follow-up time line to measure short-term and long-term maintenance of change. Our randomization procedure will help mitigate bias across the treatment groups, providing groups that are equally distributed across a number of characteristics known to influence outcomes.

Study Timeline:

The first 6 months of the project have been devoted to start up activities that have included hiring and training research assistants; finalizing data collection protocols; finalizing the CM manual, obtaining informed consent from JDC personnel and stakeholders, and collecting the first wave of drug court stakeholder measures during site visits (a more detailed project timeline, goals, and responsibilities can be found in the Budget Justification). Months 7 through 42 of the proposed study will involve data collection and CCM implementation. Months 42 through 54 will focus on completing data collection and data cleaning; and months 54 through 60 will be devoted to data analyses and manuscript preparation.

Measures:

As shown more extensively in the attached Schedule of Assessment table, different sets of measures will be collected at different time intervals (weekly, monthly, quarterly, and annually).

Version: 2017 09 06 Page 11 of 45

Measures will assess caregiver participation in JDC and adolescent drug treatment, youth outcomes, therapist fidelity, and descriptive and moderator variables. To enhance construct validity most constructs will be measured from multiple sources (e.g., caregiver report, youth report, therapist report, JDC personnel, archival records) using **reliable** and **valid instrumentation**. A copy of each measure is included with this protocol submission.

Caregiver Participation Measures. Multiple measures and multiple informants will be used to assess caregiver participation in JDC weekly status hearings and treatment sessions. Caregiver attendance in JDC will be independently recorded by the JDC supervisors or research assistant using the Parent/Caregiver Drug Court Attendance Form and collected weekly at drug court. Differences between research assistants and supervisor reports will be reconciled using court records. Drug court records will also be reviewed for caregiver and youth attendance and unexcused absences at drug court sessions. Quality of caregiver participation in drug court will be recorded using the Juvenile Drug Court Caregiver Participation Ratings form, which will be completed by a research assistant. Barriers to Drug Court participation will be measured using the Barriers to Drug Court Participation measure, which will be completed by the caregiver. Similarly, caregiver attendance at youth treatment sessions will be recorded by therapists and measured as a percent of scheduled sessions using the Caregiver Contingency Management Session Tracking Sheet (CM Group) or Caregiver Treatment as Usual Session Tracking Sheet (Treatment as Usual Group); Barriers to Treatment participation will be measured using the Barriers to Treatment Participation measure, which will be completed by the caregiver. See the schedule of assessments table below for timing of assessment.

Implementation fidelity. The 12-item Contingency Management Competence Scale (CMCS) assesses fidelity to prize-based CM procedures. The CMCS has good inter-rater reliability, internal consistency, discriminant, concurrent and predictive validity in substance abusing outpatients. In the present study, the CMCS will be used to rate CCM audiotapes. Initially, 100% of audiotapes will be reviewed to establish inter-rater reliability. Subsequently, the CMCS will be used to assess treatment fidelity. Treatment implementation will also be measured using the Caregiver Contingency Management tracking sheet, which will be completed by the therapist. The Caregiver Contingency Management tracking sheet will track number of prize draws provided to families at each session and the associated activities. To maintain balance across the treatment groups, a comparable measure will be given to the treatment as usual group, Caregiver Treatment as Usual session tracking sheet.

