Model building & estimation. The data will be analyzed using MRMs. This approach provides a variety of options for modeling change over time, including linear, non-linear, and phase-specific (e.g., during-treatment, post-treatment) patterns of change. Prior to analysis, each outcome will be graphically and descriptively evaluated to determine the best distribution for modeling. The model building approach detailed by Singer and Willett will be used to specify fixed and random effects. First, a fully unconditional model will be estimated to determine the proportion of within- and between-subject outcome variance. Second, at the repeated measurements level, and informed by the spaghetti plots, growth terms (e.g., linear, quadratic) will be specified to explain the within-subject variance. These terms will be computed using participants' actual assessment dates, tailoring the model to the observed spacing of measurements. 100 Third, the effect of CCM will be modeled by an uncentered, dichotomous indicator (i.e., CCM = 1, TAU = 0) at youth/caregiver level (i.e., level-2), and cross-level interaction effects will be specified between the CCM indicator and the level-1 growth term(s). Before estimating the final model, fixed effect indicators will be included to test for systematic differences across therapists, providers, and districts/judges, and if identified, differences will be statistically controlled in the final model. The analyses will use an intention-to-treat approach, with youth/caregivers retained in the research measurement portion of the study independently of participation in the intervention. The models will be performed using HLM software. 101 Significance tests for variance components will be based on the likelihood ratio test, tests for fixed effects will be based on the Wald test (i.e., B / SE), and 95% CIs will be computed to reflect the magnitude and precision of the effects.

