Aim 1: Evaluate whether caregivers receiving prize incentives (CCM) for attendance and participation in JDC and adolescent drug treatment show greater attendance and participation in JDC and adolescent drug treatment relative to parents not receiving CCM (i.e., JDC TAU). The data for evaluating this aim have a unique structure – caregivers will have different numbers of opportunities for attendance and participation. MRMs, however, readily accommodate this feature. The data will be structured with multiple scheduled dates for each youth/caregiver, and for each date, a value of 0 or 1 will reflect the attendance and participation status. The dichotomous attendance and participation outcomes will be modeled using a Bernoulli outcome distribution with a logit link function and Laplace approximation of the maximum likelihood function. The formulation will compare CCM and TAU on their change over time in attendance and participation. Of note, if the model building steps reveal low within-caregiver variability in attendance and participation, an unconditional level-1 model will compare CCM and TAU on the overall average level of attendance and participation.

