Aim 2: Examine whether youth whose caregivers receive prize incentives (CCM) have greater reductions in drug use and criminal re-offending relative to youth receiving treatment as usual (TAU). Aim 2 will be evaluated using a series of two-level MRMs with repeated measurements of drug use and antisocial behavior (level-1) nested within youth (level-2). For urine drug screens (UDSs), the number and spacing of measurements will vary both within and across youth. For the GAIN subscales and SRD, there will be six measurements per youth, scheduled to occur at 0, 3, 6, 9, 12, and 18 months following baseline. The archival criminal charge data, which will be comprised of charge dates within youth, will be evaluated to determine the most appropriate modeling approach. For instance, if charges occur infrequently, the outcome could be the total count of charges during the 18 month period, evaluated using a single-level generalized linear model with a negative binomial outcome distribution. Alternatively, if charges occur more frequently, the outcome could be specified as the count, or any occurrence, during time periods that correspond to the research measurements. The models for Aim 2 will test for differences between CCM and TAU on the drug use and antisocial behavior outcomes at baseline and in the rate (and/or acceleration) of change over time.

Aim 3: Examine whether caregiver attendance and participation explain condition-related changes in youth drug use and criminal offending. Aim 3 will be tested using the product of coefficients

Version: 2017 09 06 Page 20 of 45

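### The urn-randomization factors are unnamed and no Aim 1 or Aim 2 model must include them: validity is not harmed, but average-level contrasts give up some precision that costs almost nothing to keep (minor)

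*Combined protocol and SAP*

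**What the plan says.** Section 3.0.4 describes the allocation method: "The proposed urn randomization procedure is a randomization method that aims to achieve balance across groups on factors that, if unaddressed, could bias estimates". The Design Overview in section 4.0 adds that randomization is intended to reduce bias by "providing groups that are equally distributed across a number of characteristics known to influence outcomes". Neither place lists a factor or its levels, and no other section does.

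Section 7.0, under Model building & estimation, specifies growth terms. Then "the effect of CCM will be modeled by an uncentered, dichotomous indicator", together with its interactions with those growth terms. The one covariate rule reads: "fixed effect indicators will be included to test for systematic differences across therapists, providers, and districts/judges, and if identified, differences will be statistically controlled". It is not linked to the urn. The Aim 1 and Aim 2 paragraphs add no covariates. Therapeutic alliance is a required control only in the Aim 3 mediation models.

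The main Aim 1 comparison is change over time, with a contingency: "if the model building steps reveal low within-caregiver variability in attendance and participation, an unconditional level-1 model will compare CCM and TAU" on their overall average level. The repeated-measures models of Aim 2 test the baseline difference and the rate of change. For archival charges one option is given: "if charges occur infrequently, the outcome could be the total count of charges during the 18 month period". The same section says that "95% CIs will be computed to reflect the magnitude and precision of the effects".

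**The concern.** By the plan's own account the urn factors influence outcome. Balancing on them and then leaving them out of the model keeps their variance in the residual. The model-based standard error also ignores the balance that the urn has achieved. For a contrast of average levels this means a wider interval and lower power than the design could deliver.

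There is also a problem of specification. A reader cannot tell which factors the analysis should contain. If provider or judge happens to be an urn factor, a preliminary look at outcome data would decide whether a randomization factor stays in the model.

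**Working it through.** **Inputs from the documents.** 180 families in two arms (Design Overview); Aim 2 GAIN and SRD measurements at 0, 3, 6, 9, 12 and 18 months; 40% family attendance in the drug-court study cited in section 1.0; court dates that are not weekly (CCM specification). The plan states no power, effect size or alpha, so there is no figure of its own to reproduce.

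**Assumptions.** 1:1 allocation; two-sided 5% test (inferred from the 95% intervals); four binary urn factors with prevalence 0.5; one urn per factor level, drawing from the most unbalanced urn, starting with one ball per arm and adding one of the opposite arm; an effect giving about 80% adjusted power. R² is the share of outcome variance that the factors explain.

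**1. Linear level contrast, closed form.** Unadjusted power is Φ(2.80·√(1−R²) − 1.96), against Φ(0.84) = 0.80 adjusted. The ratio of unadjusted to adjusted interval width is 1/√(1−R²). At R² = 0.20, 2.80 × 0.894 − 1.96 = 0.544, so power is 0.707 and the width ratio is 1.118.

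| R² | Power | Width ratio |
|---|---|---|
| 5% | 0.779 | 1.026 |
| 10% | 0.757 | 1.054 |
| 20% | 0.707 | 1.118 |
| 30% | 0.649 | 1.195 |

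**2. Linear level contrast, simulated** (22,000 trials; Monte Carlo SE 0.15 points for size, 0.3 for power). Adjusted power is 0.794 under the urn and 0.783 under simple randomization. Adjusted size under the urn is 0.050.

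| R² | Urn: size, unadjusted | Urn: power, unadjusted | Urn: model SE / true SE | Simple: size, unadjusted | Simple: power, unadjusted |
|---|---|---|---|---|---|
| 5% | 0.048 | 0.781 | 1.01 | 0.052 | 0.775 |
| 10% | 0.044 | 0.761 | 1.02 | 0.051 | 0.753 |
| 20% | 0.039 | 0.712 | 1.05 | 0.051 | 0.702 |
| 30% | 0.035 | 0.656 | 1.08 | 0.051 | 0.642 |

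The power gap under the urn is 1.3, 3.3, 8.2 and 13.8 points. Under simple randomization it is 0.8, 3.0, 8.1 and 14.1. The gap is therefore the generic adjustment gain. Only the SE ratio and the small fall in size belong to the urn. At R² = 20%, varying the number of factors (2 to 6), the ball rules or the prevalence gave size 0.038 to 0.047 and unadjusted power 0.707 to 0.715.

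**3. Aim 1 fallback** (logit random-intercept model, intercept SD 1.2, 2,500 trials). With factors explaining 10, 20 or 30% of intercept variance, power without and with them is 0.746/0.768, 0.716/0.772 and 0.678/0.765 for 8 hearings. For 16 hearings it is 0.750/0.779, 0.715/0.784 and 0.670/0.786. Unadjusted size is 0.043 to 0.051 (Monte Carlo SE 0.004), not distinguishable from 0.05.

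**4. Total charge count** (negative binomial, dispersion 0.8, 6,000 trials). For a factor SD of 0.3 and 0.5 on the log rate, power without and with the factors is:
- 0.3 charges per youth: 0.670/0.679 and 0.646/0.662
- 0.5 charges per youth: 0.706/0.714 and 0.682/0.708
- 1.5 charges per youth: 0.741/0.759 and 0.688/0.744

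Unadjusted size is 0.043 to 0.059 and adjusted size 0.049 to 0.058. The Monte Carlo SE is √(0.05 × 0.95/6,000) = 0.003. The unadjusted values fall on both sides of 0.05, so there is no consistent conservatism.

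**5. CCM-by-time slope contrast** (six visits, complete data, 8,000 trials). If the factors shift level only, power without and with them is 0.797/0.793 and 0.801/0.796, so nothing is lost. If they explain 20% of true slope variance, it is 0.769/0.793 (slope reliability 0.4) and 0.746/0.796 (reliability 0.7), a loss of 2 to 5 points.

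**The case against.** The planned main tests concern change over time and are unaffected when the factors shift only the level. The two contrasts that are affected are contingencies that may never be used. Every magnitude rests on assumed prognostic strength and urn settings, and the plan states no power target that the omission would breach. Section 7.0 already has a route by which provider, therapist and judge can enter. All of this stands, and it is why the point is minor.

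Three stronger readings are tempting and should be resisted.

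- **Average-level tests become conservative in general.** This appears only for the linear test, which the plan names for neither contrast. The logit and negative binomial simulations do not show it.
- **The planned intervals misstate precision by 3 to 20%.** Those percentages compare unadjusted with adjusted intervals and are the generic gain. The urn-specific misstatement is the SE ratio, 1.01 to 1.08.
- **Outcome data will decide whether a randomization factor is kept.** This would be true only if provider or judge is an urn factor, and no section says so.

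It is also fair that a blanket rule to add every urn factor could go wrong. If a factor were baseline drug use, it would become a covariate in a model whose outcome series already contains T0. The fix needs an exception for that case.

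The objection does not remove the mismatch in the text: as written, the plan does not analyse by the factors it randomizes by.

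**Conclusion.** The point holds as a nearly free improvement of minor weight. The urn factors are not named, and no Aim 1 or Aim 2 model is required to contain them.

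A reader might infer that the trial's tests are therefore invalid or its main comparisons underpowered. The documents support neither. The omission alone does not inflate Type I error, and the CCM-by-time tests lose nothing unless the factors predict rate of change. This statement covers the omission only. It does not extend to the non-random placement of training families or to covariate selection by preliminary test.

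The loss is in average-level contrasts: about 1, 3 and 8 points of power at an assumed R² of 5, 10 and 20% in the linear case. It is somewhat smaller in the logit fallback (2 to 3 points at 10% of intercept variance, 6 to 7 at 20%) and about 1 to 6 points for the charge count. It is zero if the factors are not prognostic. The urn's own contribution is a linear-model SE about 1 to 5% too large over that range, and 8% at R² = 30%.

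**What to change.** In 3.0.4, name the urn factors and give their levels.

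In Model building & estimation, state that these factors enter the Aim 1 and Aim 2 models as fixed level-2 main effects, or as ordinary covariates in the single-level count model, whatever their significance. This includes provider or judge if either is an urn factor. Add one exception: a factor that is the baseline value of the modelled outcome is not added where T0 is already in the outcome vector.

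Factor-by-growth terms for the slope contrasts may be pre-specified but are optional. How to treat provider, judge or therapist when it is not an urn factor is a separate choice and can stay as it is.

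The cost is wording and a few degrees of freedom. The exact number depends on the levels once named; provider, with three agencies listed under Treatment as Usual, would take two. An urn cannot run without recording its factors, so no new data are needed.

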In addition, because youths 16 years and older can be waived to adult court for new arrests, adult arrest records will be obtained for such youths. (2) The 47-item **Self-Report Delinquency Scale** (SRD) will assess youth involvement in delinquent acts (both status and index offenses) during the past 90 days. The SRD includes an overall general delinquency scale and subscales pertaining to person offenses (e.g., assault) and property offenses (e.g., vandalism), and is considered one of the best validated self-report delinquency measures.

Adolescent mental health outcome measure. Mental health functioning will be measured based on parent report and youth report: (1) **Child Behavior Checklist** (caregiver report) and (2) the 12-item **Brief Problem Checklist** (BPC) provides an efficient and highly reliable and valid measure of youth internalizing and externalizing symptoms from caregiver and youth perspectives.

Measures of treatment acceptability. Interviews and questionnaires will be used to gather qualitative and quantitative data on treatment acceptability issues. The 47-item Survey of Counselor's Perceptions of Incentive Programs (SCPIP) measures the attitudes of treatment providers towards the use of tangible incentives and social incentives in the treatment of substance abuse problems. The SCPIP has been used with professionals involved in drug treatment including program administrators, program directors, and medical staff. The SCIPP will be completed by JDC personnel at the start of CCM and yearly, thereafter. A modified version of the SCIPP (that will be piloted during start-up) will be completed by caregivers and youth at baseline and end of CCM. In addition, caregivers and youth will complete the Client Satisfaction Questionnaire-8 (CSQ), which evaluates perceptions of the therapist and treatment. The Caregiver Satisfaction with Caregiver Contingency Management (CCM) measure (CM group only) will also be collected to gather data on caregivers who participated in the Contingency Management (CM) group assessing caregiver's perspective of the CCM program – this measure will be collected at Month 5, or end of treatment, whichever comes first.

Refinement of intervention/assessment protocols. Research assistants will conduct semistructured exit interviews (Qualitative Interview- Caregiver, Qualitative Interview- Therapist, Qualitative Interview- Youth, Qualitative Interview- Drug Court) with the caregivers, youths, therapists, and JDC personnel to assess their perceptions of intervention components, study procedures, and suggestions for research and intervention refinement. Therapists and JDC personnel will be asked about their views of CCM during each year of clinical implementation. Youth and caregivers will be interviewed separately and asked about their general opinions of drug court and CCM procedures at the conclusion of treatment. Analysis of the qualitative exit interview data will inform the refinement of CCM in terms of intervention content and delivery and will be used to plan dissemination efforts. We will collect semi-structured exit interviews from a subset (20%, n=36; randomly selected throughout the study) of families regardless of intervention attendance or treatment success. All exit interviews will follow semi-structured interview guides and be conducted in accord with standard qualitative procedures (e.g., allowing the interviewer to elaborate on relevant and important issues that emerge during the interview). Interviews will be audio recorded, transcribed, and analyzed using grounded theory qualitative methods. Given the cyclical nature of data collection and analysis in qualitative research, the guides may change during data collection to incorporate questions raised by emerging themes and issues in the interviews. [name] (Co-I) will participate in developing the interviews and overseeing their analysis, drawing from her substantial experience conducting qualitative research using grounded theory methods and teaching qualitative methods of inquiry.

Control Measures. To control for the quality of the relationship with the therapist (CCM, TAU) as a potential confound, caregivers, youth, and therapists will complete the 36-item **Working Alliance Inventory** (WAI), which measures three aspects of the therapeutic alliance; emotional bond, agreement on goals, and agreement on tasks. The WAI will be completed monthly during active treatment. To assess and control for other services the youth may receive besides research treatment conditions the caregiver will be asked during the monthly assessments if the youth received mental health or substance abuse services beyond TAU.

Additional Measures. These instruments will be used to describe the sample; some will be examined in supplemental analyses as possible moderators of outcomes. (1) **Demographics and Service**

Version: 2017 09 06 Page 13 of 45

Utilization Survey completed by caregivers and Demographics forms completed by therapists, youth, and drug court personnel, (2) The presence of substance use disorders and specific psychiatric comorbidities (e.g., anxiety, mood, disruptive behavior disorders) will be assessed by research staff using scales from the Global Appraisal of Individual Needs-Initial (GAIN-I), (3) The self-report version of the Addiction Severity Index (ASI), (4) The widely-used 21-item Beck Depression Inventory-2nd Edition (BDI-II) will assess caregiver depression, (5) Homework Rating Scale will assess parent compliance with homework, (6) Parent-Adolescent Sexual Communication scale will assess parent and adolescent perception of the quality and quantity of sexual communication, (7) Termination Questionnaire will provide information about why a family left treatment and will be completed by study therapists, and (8) Choice Questionnaire (Kirby Delay Discounting) measure, will provide information about impulsive choice — a personal characteristic CM interventions attempt to augment.

